3.2. Secondary Endpoints

The following endpoints will be also evaluated as secondary endpoints:

- Rate of Major Adverse Event (MAE) Rate in hospital and at 30 days, 1, 2 and 3 years post-procedure, defined as a composite rate of cardiovascular death, index limb amputation and ischemia-driven Target Lesion Revascularization (TLR).
- Rate of occurrence of arterial thrombosis of the treated segment.
- Rate of ipsilateral embolic events of the study limb.
- Rate of clinically-driven target lesion revascularization at 6, 12, 24 and 36 months.
- Patency rate at 12 months post-procedure, defined as freedom from clinically driven TLR and duplex ultrasonography restenosis (ultrasound peak systolic velocity ratio ≤ 2.4 or stenosis ≤50%)
- Rate of vascular access site complication defined as the combined rate of hematoma, AV fistula or a pseudoaneurysm that required intervention, such as surgical repair or transfusion, prolonged hospital stay or required a new hospital admission.
- Lesion success (per device), defined as achievement of a final in-lesion residual diameter stenosis of <50% (by QA), using any device after wire passage through the lesion. Pre- and post-dilatation of the lesion with a non-study device is considered part of assigned device treatment.
- Technical success (per device), defined as achievement of a final in-lesion residual diameter stenosis of <50% (by QA), using the CVT Everolimus-coated PTA Catheter without a device malfunction after wire passage through the lesion. Preand post-dilatation are considered part of assigned device treatment.
- Clinical success (per subject), defined as technical success without the occurrence of major adverse events during the procedure.
- Procedural success (per subject), defined as lesion success without the occurrence of major adverse events during procedure.
- Ankle-Brachial Index (ABI) changes before procedure compared with ABI at discharge and at 6 and 12 months.

Confidential Page 16 of 79

- Change in WIQ (walking impairment questionnaire) from pre-intervention at 6 and 12-months follow-up.
- Change in walking distance from pre-procedure at 6 and 12 months.
- Change in Rutherford classification grades of chronic limb ischemia from preintervention at 6 and 12-months follow-up for the treated limb.

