For a post-treatment residual stenosis >50% or significant dissection after study treatment, post-dilatation should be performed. A commercially available nitinol stent may be used to treat a flow-limiting dissection or persistent residual stenosis >50% only after post-dilatation inflation is unsuccessful. If stent post-dilatation is performed, a CVT Everolimus-coated PTA Catheter should be used.

Angiography following PTA

Angiographic imaging is to be performed according to the angiographic core laboratory protocol and will include runoff into the distal extremity. Post-procedural images should be captured in a precise manner such as was used for the pre-procedure images.

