6.2. Analysis Populations

The primary endpoints will be analyzed on the entire safety population and on the evaluable subject population, as appropriate.

The safety population will consist of all subjects who enrolled into the study and for whom the procedure had been initiated.

All effectiveness endpoints will be analyzed using the evaluable population, which consists of subjects who had no bailout procedure and at least one valid follow-up visit.

Confidential Page 34 of 79

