6.4. Statistical Analyses

Detailed analyses of the primary endpoints will be performed when all of the subjects complete their primary follow-up visit at 180 days. No effort will be made to impute or extrapolate data to replace missing values. All calculations will be based on available data with missing data excluded. Any unused or spurious data will be noted as

Confidential Page 36 of 79

appropriate in the final report.

Analysis of Primary Endpoints

The primary effectiveness endpoint of patency at six (6) months will be analyzed on a per-subject basis for the evaluable populations.

The primary safety endpoint of freedom from MAE at 6 months will be analyzed using the safety population.

For both primary endpoints (ffMAE and patency at 6 months), percentages and exact 95% confidence intervals using Clopper-Pearson's method will be calculated.

Analysis of Secondary Endpoints

All secondary endpoints will be analyzed for the per-treatment evaluable population descriptive statistics will be provided to gain better understanding of the data.

For binary variables such as MAE or technical success counts, percentages, and exact 95% confidence intervals using Clopper-Pearson's method will be calculated. For continuous variables, means, standard deviations, and 95% confidence intervals for the mean using the Gaussian approximation will be calculated. If the assumption of normality seems untenable, nonparametric summary statistics will be presented instead.

For time-to-event variables, such as time to target lesion revascularization, survival curves will be constructed using Kaplan-Meier estimates, and log rank test results will be displayed for descriptive purposes only.

Analysis of Other Data

The clinical laboratory values collected will be analyzed by tabulating the number and percentage of subjects with clinically significant changes from baseline for each parameter at each time point.

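### Technical and clinical success are analysed in a set that excludes subjects with a bailout, so both are overstated if a stented lesion counts as a technical failure.

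*Combined protocol and SAP*

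**What the plan says.** Section 6.4, on secondary endpoints: "All secondary endpoints will be analyzed for the per-treatment evaluable population". The next paragraph sets the method: "For binary variables such as MAE or technical success counts, percentages, and exact 95% confidence intervals" by Clopper-Pearson. Section 6.2 defines one evaluable population, "which consists of subjects who had no bailout procedure and at least one valid follow-up visit", and assigns all effectiveness endpoints to it. It also defines a wider set: "The safety population will consist of all subjects who enrolled into the study and for whom the procedure had been initiated". Nothing in section 6 assigns the acute success endpoints to that wider set.

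Section 3.2 defines four acute endpoints.
- Technical success (per device) is a final residual stenosis below 50%, "using the CVT Everolimus-coated PTA Catheter without a device malfunction after wire passage through the lesion".
- Lesion success (per device) uses the same threshold, but "using any device after wire passage through the lesion".
- Clinical success (per subject) is technical success with no major adverse event during the procedure.
- Procedural success (per subject) is lesion success with the same condition.

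Section 4.3 permits a nitinol stent after the study balloon for a flow-limiting dissection or for "persistent residual stenosis >50% only after post-dilatation inflation is unsuccessful". If that stent is post-dilated, the CVT catheter should be used. A stent needed after pre-dilatation but before the study balloon makes the patient a screen failure.

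Neither section 6.2 nor Appendix B defines a bailout procedure. The stent rule sits under a bail-out heading in section 4.3, and the examiner worksheet in Appendix I has a field for a bailout stent. The image list in Appendix M uses the term more widely, for a balloon, a stent or both.

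**The concern.** Technical success should show how often the study balloon does its job without rescue. As written, needing a rescue stent removes the subject from the set in which that rate is calculated. Within the set, a technical failure can arise only from a device malfunction or from a residual stenosis of 50% or more that was left unstented. Clinical success inherits the same restriction.

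Lesion success allows any device, so its gap from technical success should show how often another device was needed. Once the stented subjects are gone from both rates, that gap reflects malfunctions only.

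The follow-up condition is a separate mismatch. These endpoints are known when the procedure ends, yet a subject who dies or withdraws before any valid visit would not be counted. Section 9.6 calls this a first-in-human study, so an accurate acute performance rate is one of its useful products.

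**Working it through.** **The plan's own figure.** Section 6.3 expects about 68 evaluable subjects from 75 with roughly 10% dropout: 75 × 0.90 = 67.5, which reproduces it. That figure has no allowance for bailout exclusions.

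**The chain.**
1. Section 6.4 puts technical success in the evaluable set.
2. Section 6.2 removes bailouts from that set.
3. By the screen-failure rule in section 4.3, a bailout stent in an enrolled subject follows the study balloon.
4. One of the two reasons for such a stent is a stenosis above 50% that post-dilatation did not resolve.
5. A subject stented for that reason did not get below 50% by balloon alone.

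**Inputs.** N = 75 treated (section 6.3). Let k be the subjects stented for persistent stenosis and m the other technical failures, none of them stented. The documents give neither, so both are assumptions. One device per subject is assumed, and loss to follow-up is ignored.

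**Formulas, if each stented subject is a technical failure.**
- All treated: (75 − k − m)/75
- Evaluable set: (75 − k − m)/(75 − k)

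| k | m | All treated (exact 95% CI) | Evaluable set (exact 95% CI) |
|---|---|---|---|
| 0 | 0 | 75/75 = 100% | 75/75 = 100% |
| 4 | 0 | 71/75 = 94.7% (86.9–98.5) | 71/71 = 100% (94.9–100) |
| 8 | 0 | 67/75 = 89.3% (80.1–95.3) | 67/67 = 100% (94.6–100) |
| 8 | 2 | 65/75 = 86.7% (76.8–93.4) | 65/67 = 97.0% (89.6–99.6) |

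The 100% in the second and third rows follows from setting m = 0. The last row shows the effect when other failures occur.

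**Lesion success, k = 8 and m = 2.** Suppose the two other failures are unstented residual stenoses and all eight stented lesions finish below 50%. Lesion success is then 73/75 = 97.3% in all treated and 65/67 = 97.0% in the evaluable set, so it is not inflated. Lesion minus technical success is 73/75 − 65/75 = 8/75 = 10.7 percentage points in all treated, and 65/67 − 65/67 = 0 in the evaluable set.

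**If stented lesions can be technical successes.** Suppose instead that a stented lesion, post-dilated with the CVT catheter and finishing below 50%, counts as a success. With k = 8 and m = 2, technical success is 73/75 = 97.3% in all treated and 65/67 = 97.0% in the evaluable set. The upward shift disappears, so its direction depends on how stented lesions are classified.

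**The case against.** The strongest objection is to the classification. Section 3.2 asks for a final stenosis below 50% using the CVT catheter and does not say that the catheter must achieve it alone. It treats post-dilatation as part of the assigned treatment, and section 4.3 directs that stents be post-dilated with the same catheter. A stented lesion can therefore be argued to be a technical success. This stands: a reader might infer that the bias is upward whatever one assumes, and the documents do not support that.

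Three other stronger readings also fail.
- A reader might infer that all balloon failures leave the set. Only subjects with a bailout do; malfunctions and unstented residual stenosis stay in as failures. A stent for dissection with residual stenosis below 50% is not plainly a technical failure at all.
- A reader might infer that lesion success is inflated too. Rescued lesions count as successes there, so it is not.
- A reader might infer that these rates decide whether the device goes forward. Section 6.1 links further investigation to a trend against historical control and to the absence of safety concerns. The acute rates are descriptive and have no threshold.

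The meaning of bailout is also inferred. Under Appendix M's wider use, subjects rescued with a balloon alone would leave as well, but stented subjects would still be excluded. The evaluable set named in section 6.4 has an extra qualifier that is not defined; it is read here as the section 6.2 set.

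Mandatory pre-dilatation, with a stent at that stage a screen failure, makes a high stent rate less likely. Section 6.4 says unused data will be noted in the final report, and the Appendix I worksheet records bailout stents, so the exclusions could be traced. That softens the problem but does not correct the reported rate.

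**Conclusion.** The point holds in a limited form. Following the plan as written makes a procedure-day performance rate conditional on not having needed rescue and on having returned for follow-up. Nothing in section 6 prevents this.

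The overstatement of technical and clinical success rests on two readings: that a bailout is a stent after the study balloon, and that a lesion stented for persistent stenosis is a technical failure. Both are the more natural readings, and neither is stated. Given both, the overstatement of technical success is 5.3 percentage points at 4 stented failures in 75 (100 − 94.7) and 10.7 at 8 (100 − 89.3), with no other failures. It is zero if no subject is stented for persistent stenosis. The counts are illustrative. For lesion and procedural success, the loss is the contrast with technical and clinical success, not an inflated rate. Stented subjects remain in the primary safety analysis, which uses the safety population.

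**What to change.** - **Section 6.4:** analyse lesion, technical, clinical and procedural success in the safety population, with no follow-up visit required. For the two per-device endpoints, count all treated lesions or devices in that population.
- **Section 3.2, with the matching definitions in the protocol summary and Appendix B:** state that a lesion needing a stent for persistent stenosis above 50% after the study balloon is a technical failure, even if the stent is post-dilated with the CVT catheter. State how a stent placed for dissection alone is counted.
- **Section 6.2:** define a bailout procedure as a stent implanted in the target lesion after the study balloon. Align the Appendix M label with that definition.
- **Reporting:** give the number of bailouts.

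The cost is a few sentences and one label. The safety population already exists, and Appendix M already asks for a final angiographic run. Visits, procedure and sample size do not change. The downside for the sponsor is that reported technical and clinical success may be somewhat lower.

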1.2. Background and Literature Review

Peripheral artery disease (PAD) is associated to incident cardiovascular morbidity and mortality¹ and would have affected in 2015 about 236 million people aged 25 years and older worldwide; women accounted around 52% of this population.² Total disease prevalence has been estimated at between 3% and 10%, increasing to 15 to 20% in subjects over 70 years.³ Only about 25 percent of affected individuals undergo treatment for the disease.⁴

The most common symptom of PAD is difficulty in walking (intermittent claudication); less common is critical limb ischemia (CLI) which includes severe, persistent rest pain (requiring treatment with analgesics), ulceration or gangrene of the distal extremity. Lower extremity arterial disease can lead to reduced mobility, limb pain, gangrene and amputation, as well as increased mortality^{3, 5, 6, 7} Subjects with PAD generally also present with cardiovascular disease (CVD) which may explain the increased risk of mortality from myocardial infarction (MI) and stroke for these patients,^{6, 8, 9} with mortality rates at five years ranging from approximately 30% to 44%.^{10, 11}

The superficial femoral artery (SFA) is the most commonly diseased artery in the peripheral (lower limb) vasculature. Available therapies for patients with PAD remain controversial. Treatments include watchful waiting, medical management, endovascular treatment and surgical reconstruction.¹²

Medical management comprises risk factor modification (i.e. diabetes control, smoking cessation, hyperlipidemia lowering), exercise therapy, pharmacological therapy. ^{13, 14, 15}

Risk factor modification therapy is recommended to improve claudication and decrease the morbidity and mortality associated with the progression of PAD. Exercise therapy can produce clinical improvements in walking ability and reductions in claudication pain. ¹⁹⁻²¹ Pharmacological options include antiplatelet and anticoagulant therapies. ^{16, 17, 18}

Surgery is typically reserved for subjects with CLI and is associated with risks such as wound complication, death, MI, infection and leg edema. 18, 23 Patency rates for surgical

Confidential Page 11 of 79

revascularization of the lower extremities have been reported to be 23-74%. 18, 23, 24

During the past decade, endovascular therapy has become the primary therapy in SFA interventions.²⁵

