3. STUDY DESIGN

The CVT-SFA Trial investigates the inhibition of restenosis using the CVT Everolimus-coated PTA Catheter in the treatment of de-novo occluded/ stenotic or re-occluded/ restenotic superficial femoral or popliteal arteries. The clinical study will be a prospective, multi-center, open, single-arm study.

Each subject will be followed for at least 3 years (36 months) after treatment. All subjects will have a follow-up contact or an optional office/hospital/clinic visit at 30 days. A follow-up office/hospital/clinic visit will occur at 6 and 12 months and a follow up phone call will occur at 24 and 36 months.

To participate in this study, the site will need the resources necessary for conventional vascular surgery as well as for fluoroscopy-guided catheter-based procedures with high quality imaging.

The study participation flow chart is provided in Figure 1.

[figure not shown]

Figure 1. CVT-SFA Study Participation Flow Chart

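### MAE at 1, 2 and 3 years is planned as a simple proportion that cannot use partial follow-up, and the log-rank clause has no groups to compare

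*Combined protocol and SAP*

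**What the plan says.** - Section 3.2 lists as a secondary endpoint "Rate of Major Adverse Event (MAE) Rate in hospital and at 30 days, 1, 2 and 3 years post-procedure". The composite is cardiovascular death, index limb amputation and ischemia-driven target lesion revascularization (TLR).
- Section 6.4 gives the method: "For binary variables such as MAE or technical success counts, percentages, and exact 95% confidence intervals" by Clopper-Pearson. The opening of 6.4 says that nothing is imputed and that missing values are left out of every calculation.
- Section 6.4 plans Kaplan-Meier curves for time-to-event variables. Time to TLR is the only example, and MAE is not named there. It adds that "log rank test results will be displayed for descriptive purposes only".
- Section 3 describes the design and follow-up: "The clinical study will be a prospective, multi-center, open, single-arm study"; "Each subject will be followed for at least 3 years (36 months) after treatment"; and "a follow up phone call will occur at 24 and 36 months".
- The only loss figure is about 10%, in section 6.3, for the 6-month patency calculation. No loss is stated for 1, 2 or 3 years.

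**The concern.** A subject last contacted event-free at 14 months contributes real information about MAE risk up to 14 months and none after. A proportion at 24 or 36 months cannot represent that. The subject must be dropped, which discards 14 event-free months, or counted as free of MAE to the end, which was not observed. Section 6.4 chooses neither, so the denominator of the year-2 and year-3 rates could be settled after the data are seen. A Clopper-Pearson interval on either denominator treats it as fully followed.

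At stake is the late safety description of a device that section 9.6 calls first-in-human. The log-rank clause is a smaller matter. The test compares groups, and the plan defines none.

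**Working it through.** **The plan's own figure.** No figure is stated for MAE beyond 6 months. The nearest is the section 6.3 example with the same interval method: 11 MAEs in 75 leaves 64/75 = 85.3% free of MAE. The exact interval is 75.3% to 92.4%, as stated. The method is sound when every subject's status is known. The question is what happens when it is not.

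**Assumptions (not from the documents).** True 3-year MAE risk F = 30%; loss to follow-up by 3 years D = 10%, 20% or 30% in the absence of an event; constant hazards; loss independent of MAE; no competing death.

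**Formulas.**
- Event hazard λ = −ln(1−F)/3; loss hazard μ = −ln(1−D)/3.
- Followed to 3 years without event or loss: C = exp(−3(λ+μ)) = (1−F)(1−D).
- MAE observed before loss: E = λ/(λ+μ) × (1−C).
- Rule A, event-free losses removed and observed MAEs kept: E/(E+C).
- Rule B, everyone kept and losses counted as event-free: E.

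**Worked case, D = 20%.** λ = 0.11889 and μ = 0.07438 per year. C = 0.70 × 0.80 = 0.56. E = 0.6151 × 0.44 = 0.2707. Rule A = 0.2707/0.8307 = 32.6%. Rule B = 27.1%.

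| Lost by 3 years | Rule A | Rule B | Gap (points) |
|---|---|---|---|
| 10% | 31.2% | 28.6% | 2.6 |
| 20% | 32.6% | 27.1% | 5.5 |
| 30% | 34.2% | 25.5% | 8.7 |

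The target throughout is 30%. At 30% loss, an assumed true risk of 20% gives 23.2% against 16.9%, and a true risk of 40% gives 44.8% against 34.2%. These percentages do not depend on the number of subjects.

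**Which time-to-event estimator.** Read the 20% in the worked case as non-cardiovascular deaths instead of losses. A subject who has died can no longer have an MAE, so the true 3-year cumulative incidence is E = 27.1%. Kaplan-Meier with those deaths censored targets 30%, about 3 points too high. Cumulative incidence with that death competing targets 27.1%. Loss to follow-up should be censored and non-cardiovascular death should not.

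**Log-rank.** Section 3 gives one arm. Section 6.4 names no subgroup, stratum or reference curve, so no comparison is specified.

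**The case against.** Several points on the other side have force.

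- **Deaths are not missing data.** A reader might take the mortality in section 1.2 ("mortality rates at five years ranging from approximately 30% to 44" percent), convert it at constant hazard to 1 − 0.70^0.6 = 19% to 1 − 0.56^0.6 = 29% at 3 years, and conclude that attrition of that order is to be expected. The documents do not support this. Cardiovascular death is itself an MAE, Appendix B counts death of unknown cause as cardiovascular, and a subject who dies of another cause has known status. The mortality range is for peripheral artery disease in general, whereas the trial requires Rutherford 2 to 4 and life expectancy above 1 year. This stands in full.
- **The direction of error is not fixed.** A reader might infer that the planned estimator is biased upward. That holds only under Rule A. If every lost subject were excluded, including those with an earlier MAE, the proportion would be unbiased for non-fatal events under independent loss, at the price of discarding known MAEs. What stands is that the rule is unstated.
- **The error is small beside the precision.** It is about 1 point at 10% loss and about 3 at 20%. An exact interval for 22/75 (29%) runs from 19.4% to 41.0%. No threshold attaches to 3-year MAE, and section 6.1 calls this a feasibility trial. This bears on priority. It does not make the proportion the better method.
- **Loss may be limited.** Section 3.8 requires two consecutive missed contacts and failed calls and a letter before a subject counts as lost, and a later phone contact can recover interim events. This is fair, and is why no loss rate is asserted.
- **The wording leaves room.** The Kaplan-Meier sentence gives TLR only as an example. But MAE is the named example of a binary variable, so the proportion is the specified analysis.
- **The log-rank test is descriptive.** A reader might infer that it is impossible here. It could compare subgroups such as de novo and restenotic lesions, and one-sample forms exist. The supportable criticism is that nothing to compare is defined.

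**Conclusion.** The concern holds in a limited form. For MAE at 1, 2 and 3 years the plan specifies an estimator that cannot use partial follow-up and leaves the handling of event-free losses open. Under the stated assumptions (30% risk, constant hazards, independent loss), the two obvious denominators differ by 2.6 points at 10% loss and 8.7 at 30%, one above and one below the true value. The actual size cannot be derived from the documents.

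A reader might also infer that the plan mishandles the late-mortality question raised about paclitaxel in sections 1.2 and 7.4. That goes too far. MAE counts only cardiovascular death and combines it with amputation and TLR, so it addresses that question only in part. The 6-month primary analysis is unaffected, and no decision rests on the log-rank result. This is a worthwhile clarification of secondary, descriptive endpoints.

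**What to change.** In section 6.4:

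1. Estimate time to first MAE at 12, 24 and 36 months by cumulative incidence, with non-cardiovascular death as a competing event and loss to follow-up censored at last contact. Report 95% intervals and numbers at risk at each time.
2. Treat clinically driven TLR the same way, with all death competing.
3. Keep simple proportions with Clopper-Pearson intervals for in-hospital and 30-day MAE.
4. Delete the log-rank clause, or pre-specify the groups to be compared.
5. State how deaths that Appendix B labels vascular are classed. They sit under a heading separate from cardiovascular and non-cardiovascular death, and item 1 needs each death assigned to one side.

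The cost is mainly wording, with slightly more analysis work and intervals less simple than Clopper-Pearson. Time-to-event methods are already planned for TLR. Section 5.1 refers to adverse event start and end dates, but the case report forms are not reproduced, so the sponsor should confirm that dates are recorded for every MAE component, for death and for last contact.
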